5.0 STUDY TREATMENT

5.1 Overview

Patients will be randomly assigned in a double-blind fashion to receive either duvelisib 25mg or placebo twice daily for up to 10 days. Patients who have significant clinical improvement prior to day 10 and are going to be discharged from the hospital may discontinue the treatment early with investigator permission.

Blocks of 10 patients will be used to allocate patients to duvelisib or placebo. Due to differences in color between the duvelisib and placebo capsules, we will employ methods in this trial to maintain the blinding of the investigator to the best of our ability (e.g. having the drug dispensed by alternative personnel). If this study were to lead to a pivotal trial, matched placebos would be manufactured for such a trial.

Treatment is dosed orally and can be administered with or without food. For patients unable to administer orally, a duvelisib suspension will be administered through a nasogastric/orogastric tube. In this event, the capsule(s) will be opened and the dose will be placed in 40mL water and stirred until dissolved. The suspension should be administered using an appropriate syringe within 6 hours after preparation. Following administration, the tube should be rinsed with approximately 75 mL of water.

If a dose is missed by fewer than 6 hours, administer the missed dose right away and take the next dose as usual. If a dose is missed by more than 6 hours, the patient should not take an additional dose, but should take the next usual prescribed dose.

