10.0 REGULATORY AND REPORTING REQUIREMENTS

The entities providing oversight of safety and compliance with the protocol require reporting as outlined below. Please refer to Appendix C for definitions and Appendix D for a grid of reporting timelines.

Adverse events will be tracked from start of treatment through Day 29. All adverse events must be recorded on the toxicity tracking case report form (CRF) with the exception of:

- Baseline adverse events, which shall be recorded on the medical history CRF

Refer to the data submission schedule in Section 9 for instructions on the collection of AEs in the EDC.

Reporting requirements for Washington University study team may be found in Section 10.1. Reporting requirements for secondary site study teams participating in Washington University-coordinated research may be found in Section 10.2.

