12.0 STATISTICAL CONSIDERATIONS

This is a double-blinded randomized pilot phase II study. The purpose of this study is to provide hypothesis generating data on the efficacy and toxicity duvelisib for the treatment of COVID-19. The total accrual goal is 28 patients, approximately 14 in each arm. Blocks of 10 patients will be used to allocate patients to either duvelisib or placebo. The projected enrollment time frame is 3 months (approximately 9 patients per month).

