12.1 Determination of Sample Size

The primary endpoint is 28 day overall survival (OS). While outcomes data are still developing, observational studies in other areas demonstrate 28-day OS to be poor but highly variable, from approximately 10-40%. [12–14] The variability in outcomes makes a priori sample size calculations difficult, but as this pilot study is designed to generate hypotheses rather than show superiority, sample size considerations were based largely on feasibility and detecting a clinically meaningful effect rather than statistical significance. For duvelisib to have clinically meaningful efficacy, we estimate that 28-day OS is >60% in this patient population. Based on this assumption, a sample size of 28, 14 in each arm, would allow us to detect an improvement in 28-day OS from approximately 20% to 60%, with >80% power at a one-sided type I error of <0.20. If 28 day survival in the placebo cohort is considerably higher, for example 40%, we would only have approximately 40% power in detecting a statistical-significant difference. In either event, additional confirmatory studies that are adequately powered would be needed to more accurately assess the efficacy of duvelisib for the treatment of COVID-19.

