12.2 Statistical Analysis Plan

The primary endpoint is 28 day overall survival (OS) and will be treated as a binary outcome for the purposes of the primary analysis and will be described using descriptive statistics with the corresponding 95% confidence intervals. This will be an intent-to-treat analysis, and all patients randomized will be included in the analysis. The assumption is that all patients will be followed for at least 28 days. Patients who are lost to follow-up for any reason prior to this point will be included in the analysis and considered treatment failures and treated the same as a death. The 28 day OS of each cohort, duvelisib versus placebo, will be compared using Fisher's exact test of independence.

In addition to the primary analysis, OS will be treated as a time-to-event variable and will be described using Kaplan-Meier product limit estimators of event time curves and, if reached, medians with 95% confidence intervals. Cox proportional hazards models may be used to adjust for potential confounding effects. These analyses are considered exploratory, and we acknowledge that the proposed sample size will have low power for such adjustment.

The analyses of secondary end points are all exploratory in nature. Secondary endpoints of efficacy include: hospital and ICU length of stay and duration of ventilator (for those on a ventilator at the time of randomization), vasopressors, and renal replacement therapy. Kaplan-Meier product limit estimators of event time curves and, if reached, medians with 95% confidence intervals, and compared between cohorts using the Log-Rank test. For these analyses, patients will be censored at Day 28 or at death, whichever is earlier. Secondary end points of toxicity are viral kinetics and adverse events. The rate of viral load elevation and other adverse events of interested will be summarized using descriptive statistics and compared using Fisher's Exact tests.

Demographic and clinical characteristics of the sample and of each cohort will be summarized using descriptive statistics. For continuous variables, the number of patients, mean, standard deviation, median, minimum, maximum, and quartiles will be provided. For categorical variables, the number and percent of patients in each demographic/characteristic category will be summarized with 95% confidence intervals.

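### Adverse events are compared only as crude proportions to Day 29, so if survival differs between arms the comparison of non-fatal events mixes toxicity with survival

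*Combined protocol and SAP*

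**What the plan says.** Section 12.2 (Statistical Analysis Plan) gives the whole comparative safety analysis in one sentence: "The rate of viral load elevation and other adverse events of interested will be summarized using descriptive statistics and compared using" Fisher's exact tests. Fisher's test takes the number of patients with and without an event, so the word rate here means a proportion.

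Section 10.0 sets the window: "Adverse events will be tracked from start of treatment through Day 29". Section 5.1 has patients randomised "to receive either duvelisib 25mg or placebo twice daily for up to 10 days", so well over half of the window falls after the last dose.

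Section 12.0 states that "The total accrual goal is 28 patients, approximately 14 in each arm". Section 12.1 puts background 28-day survival at about 10-40% and says the sample size would allow the trial to "detect an improvement in 28-day OS from approximately 20% to 60"%, "with >80% power at a one-sided type I error of <0.20".

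Section 12.2 does censor at death or Day 28, but that rule is written for the length-of-stay and duration endpoints. We found no person-time denominator, time-to-first-event analysis or on-treatment window for adverse events. Section 12.2 calls all secondary analyses exploratory and sets neither a significance level nor a direction for the adverse-event tests.

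**The concern.** A patient who dies on Day 5 has about 5 days in which a non-fatal event can be recorded; a survivor has about 28. Where most patients may die, death is a major reason that adverse-event observation ends. If the arms differ in survival, they differ in observation time, and a crude proportion cannot separate more toxicity per day from more days alive.

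Safety and tolerability is the secondary objective, and Section 12.0 gives hypothesis-generating data on toxicity as part of the trial's purpose. The adverse-event percentages are likely to be carried into the planning of any later trial. If duvelisib lengthens survival, they would overstate its toxicity per day at risk; if it shortens survival, they would understate it.

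**Working it through.** **Inputs from the documents.** 14 per arm; 28-day survival S of 20% versus 60%, and 40% versus 60% (Section 12.1); window to Day 29, taken as T = 28 days; dosing up to 10 days (Section 5.1).

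**Assumptions.** The documents give no adverse-event rate. I take a constant first-event hazard h of 2%, 3% or 5% per day, equal in both arms unless stated, and a constant death hazard.

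**The plan's own figure.** Exact enumeration of Fisher's one-sided test at 0.20 with 14 per arm gives power of 82.7% for 20% versus 60% (stated: above 80%) and 40.1% for 40% versus 60% (stated: about 40%). Both reproduce.

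**Time alive.** The death hazard is d = -ln(S)/28, which is 0.0575 per day at 20%, 0.0327 at 40% and 0.0182 at 60%. Mean days alive to Day 28 are (1 - S)/d:

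- 20%: 0.80/0.0575 = 13.9
- 40%: 0.60/0.0327 = 18.3
- 60%: 0.40/0.0182 = 21.9

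The ratio is 1.58 at 60% versus 20% and 1.20 at 60% versus 40%.

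**Crude proportion with an event.** P = h/(h + d) × (1 - exp(-(h + d)T)). With h = 0.03 and T = 28:

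- S = 20%: 0.343 × (1 - 0.086) = 31.3%
- S = 40%: 0.478 × (1 - 0.173) = 39.6%
- S = 60%: 0.622 × (1 - 0.259) = 46.1%

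With identical toxicity per day, the longer-lived arm shows 14.7 points more at 20% versus 60% survival and 6.5 points more at 40% versus 60%. The gap is zero when survival is equal. At 20% versus 60%, the proportions are 22.9% versus 34.4% for h = 2% and 44.2% versus 62.4% for h = 5%.

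**Dosing window only.** With T = 10, h = 0.03 and 20% versus 60% survival: 0.343 × (1 - 0.417) = 20.0% versus 0.622 × (1 - 0.617) = 23.8%, a gap of about 4 points.

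**How often Fisher's test reacts.** At 20% versus 60% survival with equal event hazards, a two-sided 0.05 Fisher test with 14 per arm rejects 5.1%, 6.3% and 7.7% of the time for h = 2%, 3% and 5%, nearly always against the longer-lived arm. With equal survival of 40% it rejects about 2%.

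**Masking.** Suppose duvelisib has the higher event hazard (3% versus 2% per day) and survival is 20% on duvelisib versus 40% on placebo. Placebo: 0.02/0.0527 × (1 - exp(-0.0527 × 28)) = 29.3%. Duvelisib: 31.3%, as above. If both arms had 40% survival, the same hazards would give 29.3% versus 39.6%. The apparent excess falls from 10.3 points to 2.0.

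**What a rate would show.** Expected days at risk per patient are P/h. At h = 0.03 that is 0.313/0.03 = 10.4 days at 20% survival and 0.461/0.03 = 15.4 at 60%. Over 14 patients, about 4.4 events in 146 patient-days and 6.5 in 215 both give 3.0 per 100 patient-days, so the rate ratio is 1.

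**The case against.** The strongest reply is that the crude proportion is not wrong. With complete follow-up to death or Day 29 it is a valid cumulative incidence in the presence of death. It answers how many patients had an event, and 28-day survival is reported beside it as the primary endpoint. This stands, and it is why the rate should be added and not put in place of the crude comparison.

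Four stronger readings are tempting, and the documents do not support them.

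- *Follow-up will be very unequal.* It is unequal only if survival differs; at 40% versus 60% the effect is modest.
- *A lethal arm would look safer.* The sign reverses in the example only if placebo survival is 60% (34.4% placebo versus 31.3% duvelisib). Section 12.1 expects 10-40%, and at 40% versus 20% there is no reversal. Appendix C also counts death as a serious outcome, so the point concerns non-fatal events.
- *The test would falsely signal harm about 31% of the time.* That figure (h = 3%, 20% versus 60%) uses the one-sided 0.20 level, which Section 12.1 sets only for survival. At two-sided 0.05 it is 6.3%.
- *The direction is certain.* Section 7.0 has laboratory tests daily for inpatients but allows outpatient follow-up by telephone without them. That lowers detection of laboratory events among discharged survivors and can pull the other way.

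Viral load elevation is also less exposed than the Day 29 window suggests. Its criterion in Section 5.4 depends on day-to-day change, and Section 7.0 samples daily only through Day 10, then weekly.

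**Conclusion.** The concern holds in a limited form. Section 12.2 has no time-at-risk measure for adverse events in a trial that expects heavy mortality. If survival differs, crude proportions of non-fatal events mix toxicity with survival: about 12 to 18 points of spurious difference at the sized-for contrast for event hazards of 2-5% per day, 6.5 points at 40% versus 60% for 3% per day, and none with equal survival. The damage is mainly to the descriptive percentages, since a 14-per-arm Fisher test seldom rejects.

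These sizes rest on constant hazards, assumed event rates and equal detection in both arms. Events that cluster in the dosing window would give a smaller gap. The sample size and the primary test are unaffected. This is a worthwhile, inexpensive improvement to an exploratory analysis.

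**What to change.** In Section 12.2, keep the crude counts and Fisher's tests, and add:

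- by arm, the first-event rate per 100 patient-days at risk (start of treatment to first event, death, withdrawal or Day 29, whichever is earliest), with exact Poisson confidence intervals and a rate ratio;
- the same for the Day 1-10 dosing window;
- the number of deaths without an event, beside each crude proportion;
- for viral load elevation, a comparison restricted to the daily-sampled period through Day 10, with sampled days as the denominator.

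The cost is a few sentences and a little programming, with no new visits. Onset dates must be recorded for all adverse events: Section 10.0 names a toxicity form without listing its fields, and an event start date appears only on the serious-event cover sheet in Appendix E. The rates assume a roughly constant hazard within each window, which is the reason for the separate Day 1-10 summary. With about 4 to 7 expected events per arm in the 3% per day example, the intervals will be wide. The rates will not correct for reduced laboratory testing after discharge, which should be stated as a limitation.

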2.3 Objectives and Endpoints Table

Objectives	Endpoints	Justification for Endpoints
Primary		
To evaluate the efficacy of duvelisib for the treatment of COVID-19 disease manifestations.	Primary: 28 day overall survival	The expected survival of these patients with advanced COVID-19 symptoms is poor and studies are currently needed.
	Secondary: Hospital and ICU length of stay and duration of ventilator, vasopressors, and renal replacement therapy	In addition to improving survival, duvelisib may reduce the need for these interventions.
Secondary		
To evaluate the safety and tolerability of duvelisib for the treatment of COVID-19 disease manifestations.	Viral kinetics	Duvelisib and similar treatments which modulate cytokine signaling have the potential to reduce immune function which could result in increasing viral loads.
	Adverse events	Adverse events are common with duvelisib for its indicated purpose. It is unclear if similar adverse events are observed in this population.

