5.2 Dose Modifications

Participants will be evaluated for toxicity according to the Common Terminology Criteria for Adverse Events (CTCAE) of the National Cancer Institute (NCI) version 5.0. Dose modifications for treatment-emergent adverse events are listed in the table below. If the dose is reduced for toxicity, escalation may occur at the discretion of the treating physician following resolution/stabilization of the toxicity.

Treatment-Emergent Adverse Event	Management for Duvelisib/Placebo
Neutropenia	
Grade \leq 3	No change.
Grade 4	Hold treatment until \leq Grade 2. When resumed, reduce treatment by one dose level.
Thrombocytopenia	
Grade \leq 3	No change.

Grade 4	Hold treatment until \leq Grade 3. When resumed, reduce treatment by one dose level.
Anemia	
Any	Dose delay is not required for anemia, unless deemed necessary by the treating physician. Transfusions and/or erythrocyte stimulating agents are allowable.
Pneumonitis	
Grade 1	No change.
Grade 2	If suspected related to treatment, treat with systemic steroid therapy and hold treatment until \leq Grade 1 OR patient returns to baseline (where patient had a predetermined abnormal baseline). When resumed, reduce treatment by one dose level. If unrelated to treatment, no change unless deemed necessary by the treating physician.
Grade \geq 3	Discontinue.
Viral Load Elevation	
Increase in viral load of >0.5 log on two consecutive days, or >1 log increase in one day	See section 5.4. If viral load elevation is suspected to be related to treatment, hold treatment until patient returns to baseline (where patient had a predetermined abnormal baseline). Permission required from the principal investigator prior to re-treatment. If resumed, reduce treatment by one dose level.
All other events	
Grade \leq 2	No change.
Grade 3	If suspected related to treatment, hold treatment until \leq Grade 1 OR patient returns to baseline (where patient had a predetermined abnormal baseline). When resumed, reduce treatment by one dose level. When resumed, reduce treatment by one dose level. If unrelated to treatment, no change unless deemed necessary by the treating physician.

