5.4 Viral Load Monitoring

All patients will have three consecutive days of viral load monitoring prior to receiving duvelisib, on Screening day, Day -1, and Day 1 (see Section 7.0), to establish the baseline viral load and trend. For patients with an increase in viral load of >0.5 log on two consecutive days, or >1 log increase in one day, clinical judgement should be used to determine if any continued rising viral load is suspected to be related to study treatment. If suspected to be related to study treatment, follow dose modifications as outlined in section 5.2. If thought to be unrelated to study treatment, i.e. keeping with baseline trend, no change unless deemed necessary by the treating physician.

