7.0 SCHEDULE OF ASSESSMENTS

	Screening ¹	Study Treatment Days											Safety Follow-Up ¹¹	
		-1	1	2	3	4	5	6	7	8	9	10	15	29
Informed Consent	X													
Medical History	X													
Physical Exam w/ vital signs and O2 saturation ²	X	X	X	X	X	X	X	X	X	X	X	X	X	X
APACHE II Score		X										X		
SOFA Score		X										X		
CBC ²	X	X	X	X	X	X	X	X	X	X	X	X	X	X
CMP ²	X	X	X	X	X	X	X	X	X	X	X	X	X	X
Ferritin ²	X	X	X	X	X	X	X	X	X	X	X	X	X	X
D-Dimer ¹⁰	X		X	X		X				X			X	X
aPTT and PT/INR ¹⁰	X		X	X		X				X			X	X
Fibrinogen ¹⁰	X		X	X		X				X			X	X
C-reactive peptide ²	X	X	X	X	X	X	X	X	X	X	X	X	X	X
SARS-CoV-2 viral load ³	X	X	X	X	X	X	X	X	X	X	X	X	X	X
Quantitative immunoglobulins (IgA, IgG, IgM)	X													
Immune competence assessment	X													X
CMV IgG	X													
CMV DNA PCR (CMV seropositive pts)	X									X ⁸				
Serum βhCG ⁴	X													
Chest X-ray ⁵	X													
Electrocardiogram ⁵	X													
ECHO or MUGA ⁵	X													
Plasma troponin and NT-proBNP ⁵	X													
Duvelisib/placebo ⁶			X	X	X	X	X	X	X	X	X	X		
PJP prophylaxis ⁷			X	X	X	X	X	X	X	X	X	X	X	X

Correlative studies ⁹	X ¹²			X		X				X		X	X	X
Adverse event monitoring			Continuously											

- 1 – Within 7 days of registration
- 2 – Performed daily while inpatient or per local SOC. If outpatient, visits may occur within +/- 2 days from schedule
- 3 – Performed daily through Day +10 then weekly thereafter by NP or OP
- 4 – Women of childbearing potential only
- 5 – Not required at Screening if patient meets Inclusion Criterion 1 by other measures. Repeated on study if clinically indicated.
- 6 – Duvelisib or placebo will be administered twice daily for up to 10 days. See section 5.0 for treatment administration details.
- 7 - Continued until CD4+ T cells >200 cells/μL. Choice of agent per institutional guidelines and patient tolerance.
- 8 – CMV viral load monitoring should occur at screening, and on D8 in patients who are CMV seropositive (positive IgG at screening). CMV prevention/treatment should follow institutional guidelines.
- 9 – Collected on the first 10 patients enrolled onto study. A variance of +/- 2 days for correlative collection will be permitted.
- 10 – Performed as scheduled or more frequently if clinically indicated for coagulopathy monitoring

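### Section 12.2 analyses viral kinetics only as a yes/no elevation rate, which suits the safety concern about rising loads but has low power for slower viral clearance

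*Combined protocol and SAP*

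**What the plan says.** Section 12.2 lists viral kinetics as a secondary endpoint of toxicity. The only analysis it names is this: "The rate of viral load elevation and other adverse events of interested will be summarized using descriptive statistics and compared using" Fisher's exact tests. No slope, area under the curve, time to clearance or other repeated-measures analysis of viral load appears anywhere. The Kaplan-Meier and log-rank methods in 12.2 are for length of stay and durations of organ support. The section also states: "The analyses of secondary end points are all exploratory in nature".

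Section 2.3 gives the reason for the endpoint: duvelisib and similar drugs "have the potential to reduce immune function which could result in increasing viral loads".

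The data are serial. Section 5.4 takes three pre-dose values "to establish the baseline viral load and trend", and a note to the Section 7.0 schedule says of the swabs: "Performed daily through Day +10 then weekly thereafter by NP or OP".

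The term used in 12.2 is also a row of the dose-modification table in Section 5.2, with this threshold: "Increase in viral load of >0.5 log on two consecutive days, or >1 log increase in one day". Section 5.4 repeats it. Section 12.2 does not refer to either.

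**The concern.** The protocol collects a viral trajectory, but the analysis keeps one bit of it per patient. A patient whose load falls more slowly, or stays flat, seldom crosses a threshold built to catch a rise. Impaired viral control could show itself in just that way. Section 1.5 raises clearance from the other side, since it hypothesises that duvelisib limits viral persistence.

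The trial's stated purpose is to generate hypotheses on efficacy and toxicity before confirmatory studies. For that purpose, a between-arm difference in log/day with a confidence interval says what has and has not been excluded. A Fisher p-value on 14 v 14 yes/no outcomes says little about clearance. The count also takes no account of how many swabs each patient gave, so a patient who lives longer has more chances to meet the rule.

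**Working it through.** **1. The plan's own power figure.** The documents give no power for viral kinetics. The only calculation is for 28-day survival in Section 12.1, "with >80% power at a one-sided type I error of <0.20". With 14 per arm, the one-sided Fisher test at 0.20 has exact power 82.7% for 20% v 60% and 40.1% for 40% v 60%. Both match the stated figures (over 80%, about 40%), so 12.1 reproduces.

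**2. How much data there is.** Screening, Day -1 and Days 1-10 make 1 + 1 + 10 = 12 loads per patient, and 12 × 28 = 336 at most. Deaths lower this. With exponential deaths at the 12.1 survival rates, expected swabs over Days 1-10 are the sum over d = 0 to 9 of S^(d/28). For S = 0.6 this is 9.2 (duvelisib), and for S = 0.2 it is 7.8 (placebo). Discharge thins them further: Section 5.1 says improving patients "going to be discharged from the hospital may discontinue the treatment early".

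**3. What Fisher's test needs, with no viral assumption.** The one-sided p for x elevated on duvelisib, with m elevated in total, is the sum over k ≥ x of C(14,k)·C(14,m−k)/C(28,m). With 4 of 14 elevated on placebo:

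| Duvelisib | Two-sided p | One-sided p |
|---|---|---|
| 7 | 0.440 | 0.220 |
| 8 | 0.252 | 0.126 |
| 10 | 0.057 | 0.028 |
| 11 | 0.021 | 0.011 |

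So 11 are needed at two-sided 0.05, or 8 at one-sided 0.20. The latter is the only alpha in the documents, and it is set for survival, not for this endpoint.

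**4. Power by simulation.** All viral inputs are assumptions: starting mean 6 log (SD 1), no detection floor, swab noise SD 0.3-0.7 log, between-patient slope SD 0.1-0.3 log/day. Deaths follow 12.1. The slow-clearance case has mean slopes of 0 v −0.2, or −0.1 v −0.3 log/day. The rise case has +0.2 v −0.2. The day-to-day reading of the rule counts any one-day rise above 1 log, or two successive daily rises above 0.5. The baseline reading counts loads more than 0.5 above the pre-dose mean on two consecutive days. Power at two-sided 0.05, with one-sided 0.20 in brackets:

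| Case | Fisher, day-to-day | Fisher, from baseline | Per-patient slopes |
|---|---|---|---|
| 0.2 log/day slower | 0-19% (3-56%) | 0-24% (9-66%) | 33-99% (76-100%) |
| True rise | 28-60% (71-92%) | 28-99.6% (71-100%) | 85-100% (99-100%) |

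A repeat run in similar settings gave slopes 30-98% against Fisher 0-18% for slow clearance at two-sided 0.05.

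**5. Less favourable inputs.**
- *Low starting loads* (floor 2 log, values set to the floor, two-sided 0.05). At starting mean 3.5, slopes have about 19-60% and Fisher 0-19%. At mean 3, slopes have 20-34% and Fisher 11-12%.
- *Smaller difference.* With clearance halved from 0.3 to 0.15 log/day, floor 1 log and up to 30% stopping swabs early, slopes have 19-68% and Fisher 0-6% at two-sided 0.05. At one-sided 0.20 the figures are 59-95% and 0-31%.
- *A fitted mixed model* (random intercept and slope, pre-dose values included, 0 v −0.2). At noise 0.5 and slope SD 0.1, 0.2 and 0.3, power is 99%, 75% and 53%. At noise 0.7 and slope SD 0.3 it is 45%. If fast clearers tend to be discharged on Days 6-10, these become 98%, 70%, 52% and 41%. Interval half-widths are 0.09-0.22 log/day. Left-censoring was not simulated.

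**6. Effect of unequal follow-up.** With no viral effect, the survival gap in 12.1 alone makes the elevation rate 0-10 percentage points higher on duvelisib, because its patients give more swabs. With equal survival the gap is within 1 point. Part of Fisher's power for a rise also comes from this: with 60% survival in both arms, the day-to-day figure drops from 28-60% to 13-47%.

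**The case against.** The strongest reply is that the endpoint answers the question it was set. Section 2.3 places viral kinetics under safety because loads might increase, and an elevation rate addresses that. The persistence hypothesis in 1.5 is not carried into any objective. This stands, and it is why the count should stay. It does not explain why an endpoint called viral kinetics, sampled daily, should have no trajectory summary at all.

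A reader might infer that elevation is undefined. The documents do not support that. The Section 5.2 table carries the rule under the same term, and 12.2 speaks of viral load elevation alongside other adverse events. What is missing is a cross-reference and a statement of whether the 0.5 log criterion is measured day to day or from baseline. The second reading is plausible, since 5.4 establishes a baseline and 5.2 holds drug until return to it.

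The gain from slopes is also uncertain. Every viral input is assumed. Section 1.1 says viral load peaks days before symptoms do, so critically ill patients may start near the detection floor, where the advantage shrinks. Dose holds and reductions after a suspected related elevation can bend a trajectory back and dilute a single linear slope; a first-crossing count does not suffer from this, and no simulation here models it. These limits stand. In every slow-clearance setting tried, slopes still had more power than the count.

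**Conclusion.** The point holds as a matter of efficiency. Section 12.2 uses a method that fits a rise and can show a clear one, but it discards most of the serial data and would often miss slower clearance. For clearance 0.2 log/day slower at two-sided 0.05, Fisher's test has about 0-24% power across both readings of the rule. Per-patient slopes have about 30-99% with high starting loads and about 20-60% near the detection floor. The ranking was consistent across the settings tried; the size of the gap rests on noise, slope variation and starting load, none of which the documents give.

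Two stronger readings should be resisted. One is that the trial will present a non-significant elevation rate as proof of preserved viral control. Nothing in the documents says so, and 12.1 and 12.2 call for confirmatory studies and label the secondary analyses exploratory. The other is that a slope analysis would settle the matter. With a half-width of up to 0.22 log/day, an interval centred on a 0.2 log/day difference would still include zero. The primary analysis of 28-day survival is not touched. This is a worthwhile improvement, not a defect that threatens the trial.

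**What to change.** In Section 12.2:

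1. Cross-refer elevation to the rule in 5.2 and 5.4, and state whether the 0.5 log criterion on two consecutive days is measured day to day or from the pre-dose baseline.
2. Keep the Fisher comparison as the safety count, reported with the number of swabs per patient in each arm.
3. Add one exploratory analysis, for example:

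> Log10 SARS-CoV-2 viral load through Day 10 will be compared between assigned arms in a repeated-measures model, with the Screening, Day -1 and Day 1 pre-dose values as baseline and values below the assay detection limit treated as left-censored. The between-arm difference in slope (log/day), or in mean change from baseline by day, will be reported with a 95% confidence interval. Dose holds, deaths and discharges will be listed by day and arm.

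Mean change by day is the safer summary if dose holds are common, because it does not force one straight line.

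The cost is plan wording only: no new visit, swab or patient. The assay detection limit must be stated. Swabs missing after death or discharge are informative and remain a limitation of the model, dose holds can bend trajectories, and with 28 patients the estimate may be imprecise.
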